## 5.2 Blinding and Unblinding

Glass slides and digital images of slides scanned for each case will be de-identified and coded with a unique study identification number to ensure confidentiality. De-identification will occur per institutional policies/procedures and will follow ‘honest-broker’ policies or comparable institutional practices. All case identification numbers will be unlinked to patient identity and will not be individually identifiable by the reading pathologists.

Reading pathologists will also be blinded to original diagnoses.

## 6. SAMPLE SIZE AND POWER CONSIDERATIONS

Sample size and power considerations are based upon agreement between the diagnoses determined using Glass and WSI compared with GT.

Let  $l = 1, 2, \dots, c = 4$  index the number of sites.

Let  $i = 1, 2, \dots, n_l$  index the  $n_l$  cases/slides in site  $l$ .

Let  $j = 1, 2, \dots, r = 4$  index  $r$  pathologists who read each case from site  $l$ .

Let  $k = 1, 2$  index the new ( $k = 1$ ; WSI) and reference ( $k = 2$ ; Glass) method.

Let  $u_{li}$  = Ground Truth diagnostic classification for the  $i$ -th case in site  $l$ .

Let  $y_{lijk}$  = diagnostic classification for the  $i$ -th case by the  $j$ -th reader with the  $k$ -th method in site  $l$

Let  $g_{lijk} = \{(y_{lijk} - u_{li})\}$  and let  $a_{lijk} = \begin{cases} 1 & \text{if } g_{lijk} = 0 \\ 0 & \text{if } g_{lijk} \neq 0 \end{cases}$

Thus,  $a_{lijk} = 1$  if  $y_{lijk}$  and  $u_{li}$  are identical (no discordance [agree] or minor discordance) and  $a_{lijk} = 0$  if  $y_{lijk} \neq u_{li}$  (major discordance).

Let the difference between method 1 (WSI) and method 2 (Glass) for the proportion of readers with classifications identical or minor discordance compared to the GT classification for case  $i$  in site  $l$  be denoted by

$$d_{li} = \frac{\sum_{j=1}^r (a_{lij1} - a_{lij2})}{r}$$

Assuming  $E\{d_{li}\} = \Delta$  and variance  $Var\{d_{li}\} = \sigma^2$  (where  $d_{li}$  is equal to average over differences of error rates between WSI and Glass compared to GT diagnosis for case  $i$  in site  $l$ ) the following expression is applicable:

$$n = \frac{(Z_\alpha + Z_\beta)^2 (\sigma^2)}{(\delta + \Delta)^2} \Big/ \frac{(Z_\alpha + Z_\beta)^2 \pi'_{WSI} (1 - \pi'_{WSI}) \pi'_{Glass} (1 - \pi'_{Glass}) \{1 - \lambda + (r - 1)(\xi - \eta)\}}{r(\delta + \Delta)^2}$$

For which  $\pi'_{WSI}$  and  $\pi'_{Glass}$  are the probabilities that WSI and Glass methods agree (or minor discordance) with the GT diagnosis classification retrospectively and  $\lambda = \text{Corr}(a_{lij1}, a_{lij2})$  is the correlation between the classifications for the two modalities by the same reader and  $\xi = \text{Corr}(a_{lijk}, a_{lij'k})$  is the correlation between two readers for a given modality and  $\eta = \text{Corr}(a_{lij1}, a_{lij'2})$  is the correlation between two modalities and between two readers.

Assuming power =  $(1 - \beta) = 0.90$ ,  $\alpha = 5\%$  two-sided, a non-inferiority margin of  $\delta$ , a true difference between proportions of WSI and Glass equal to  $\Delta$  in favor of Glass, number of readers  $r = 4$  and number of sites = 4, the required sample size is provided in **Table 2** for different ranges of  $\pi'_{WSI}$ ,  $\Delta$ ,  $\lambda$ , and  $(\xi - \eta)$ .

**Table 2: Sample Size for 4 Readers per Site and 4 Sites**

$\pi'_{WSI}$	$\lambda$	$(\xi-\eta)$	$Max \sigma^2$ ( $\sigma^2$ for $\Delta=0$ )	$\Delta = \pi'_{WSI} - \pi'_{Glass}$				
				0.0	-0.5%	-1.0%	-1.5%	-2.0%
0.6	0.5	0.150	0.114000	749	976	1326	1904	2968
		0.125	0.105000	690	899	1221	1754	2733
		0.100	0.096000	631	822	1116	1604	2499
	0.6	0.150	0.102000	670	874	1186	1704	2655
		0.125	0.093000	611	796	1082	1553	2421
		0.100	0.084000	552	719	977	1403	2187
0.7	0.5	0.150	0.099750	665	852	1154	1653	2568
		0.125	0.091875	604	785	1063	1522	2366
		0.100	0.084000	552	718	972	1392	2163
	0.6	0.150	0.089250	587	762	1032	1479	2298
		0.125	0.081375	535	695	941	1348	2095
		0.100	0.073500	483	628	850	1218	1893
0.8	0.5	0.150	0.076000	500	646	871	1241	1920
		0.125	0.070000	460	595	802	1143	1768
		0.100	0.064000	421	544	733	1045	1616
	0.6	0.150	0.068000	447	578	779	1111	1718
		0.125	0.062000	408	527	710	1013	1566
		0.100	0.056000	368	476	642	915	1414

This table shows, a total of 2000 cases will provide more than 90% power to demonstrate non-inferiority of WSI to Glass with a non-inferiority margin of 4% as long as the proportion of agreements with Ground Truth is at least 60%,  $\lambda$  is at least 0.5,  $(\xi-\eta)$  is at most 0.15, and  $\Delta \geq -1.5\%$ .

## 7. DETERMINATION OF PROTOCOL DEVIATIONS

Site personnel will document all protocol deviations and device deficiencies with clear explanations. Study processes, including wash out, modality read order and matching of slides with correct case information will be closely managed. A deviation will be filed for any enrolled case part that has missing, damaged or broken slides. These cases will be reviewed for consistency with the protocol across all reading pathologists. Protocol deviations will be evaluated before locking the database and unblinding the study. The deviations will be summarized and reported.

## 8. DISCORDANCE WITH GROUND TRUTH DIAGNOSIS

Diagnoses rendered by the Reading Pathologists at each site and captured on the EDC checklists will be compared directly to the GT diagnosis. Two adjudicators will independently review the reading to determine whether the Reading Pathologist's diagnosis and the GT diagnosis are 'concordant', 'minor discordant' or 'major discordant'. If there is a disagreement involving a major discordant status between the two adjudicators, the reading will go to a third member for further adjudication. Based on the determination of the

third member, the majority choice will be selected, or a meeting will be convened to discuss the reading and determine a consensus opinion. For the purpose of this study, the definitions of major and minor discordances are as described in Table 3:

**Table 3: Definition of Discordance**

Severity	Definition 13 14
Minor	No Harm:  Will not result in harm  No change in prognosis or a change in prognosis that is unlikely to result in a change in treatment according to standard care.
	Minimal Harm [Grade 1]  Further unnecessary noninvasive diagnosis test(s) performed [e.g., blood tests or non-invasive radiological examination].  Delay in diagnosis or therapy of < 6 mos.  Minor morbidity due to [otherwise] unnecessary further diagnostic effort(s) or therapy predicated on the presence of [unjustified] diagnosis.
Major	Moderate Harm [Grade 2]  Further unnecessary invasive diagnostic test(s) [e.g., tissue biopsy, re-excision, angiogram, radionuclide study or colonoscopy].  Delay in diagnosis or therapy of > 6 mos.  Major morbidity lasting < 6mos due to [otherwise] unnecessary further diagnostic effort(s) or therapy predicated on the presence of [unjustified] diagnosis.
	Severe Harm [Grade 3]  Loss of life or limb, or other body part, or long-lasting morbidity [lasting > 6mos.].

## 9. ANALYSIS POPULATION

### 9.1 All-Available Population (AAP)

The All-Available Population (AAP) includes all cases for which at least one reader provides an evaluable outcome for either WSI or Glass modalities.

Unless otherwise specified, All Available Population (AAP) will be used for all analysis.

## 10. STUDY CASES

### 10.1 Pathologist Experience

Reader information (years of experience post-residency, average number of cases per year, type of pathologist) will be tabulated by site and overall using descriptive statistics.

### 10.2 Disposition of Cases

The number of cases screened, eligible and enrolled will be tabulated by site and overall. The reasons for non-inclusion in analysis will be provided by site and overall.

The deferrals (e.g., deferral to specialist, deferral to glass, etc.) will be summarized by reader, site and overall for each modality. The reason for the deferral will also be provided in a listing.

The number and percentage of cases included in AAP will be summarized by site and overall.

The number and percentage of AAP cases read by each reader will be summarized for each site, if the full number of cases is not read.

### **10.3 Demographics and Other Baseline Characteristics**

Information about the cases to be summarized descriptively are age and sex. Sex will be summarized overall and by site as frequency and percentages. Age will be similarly summarized as mean, standard deviation, median, minimum and maximum.

### **10.4 Ground Truth Diagnoses**

The final coded GT diagnosis obtained from the charts will be tabulated by site and overall. Information to be tabulated includes the number and percentage of cases in each of the FDA Organ, and case subtype/procedure combinations as specified in **Table 1**.

For evaluation of the GT diagnosis in the WSI modality, the reasons for re-scans of the image that were required will be tabulated by site and overall.

## **11. STATISTICAL ANALYSIS**

### **11.1 Primary Objective Analysis**

#### **11.1.1 Hypothesis and Endpoint**

To demonstrate that the effectiveness of WSI using Hamamatsu NanoZoomer Digital system is non-inferior to the diagnostic reference standard glass diagnosis in routine surgical pathology cases with a non-inferiority margin of 4%, the null hypothesis,  $H_0: \pi_{WSI} - \pi_{Glass} > 0.04$  must be rejected in favor of the alternative hypothesis  $H_1: \pi_{WSI} - \pi_{Glass} \leq 0.04$ , where  $\pi_{WSI}$  and  $\pi_{Glass}$  are the major discordance rates for WSI and Glass respectively compared to GT.

#### **11.1.2 Primary Analysis of Non-inferiority of WSI Relative to Glass**

##### Primary Analysis Model

The primary analysis of the adjudicated comparison of each modality to the GT diagnosis will be performed using a repeated measures logistic regression model. In this model, the dependent variable is major discordance status, yes versus no. Modality (Glass or WSI), will be included in the model as fixed effect; and, site, reader, and case will be included as random effects. The AAP will be used for the primary analysis; however, any reading classified as “deferred” or as missing data will be excluded. The mixed model repeated measure (MMRM) logistic regression model can be written as:

$$\text{Ln} \left[ \frac{P(Y_{ilfh} = 1)}{1 - P(Y_{ilfh} = 1)} \right] = \mu + \alpha_i + s_l + r_{f(l)} + \beta_{h(l*j)} + \varepsilon_{ilfh} \quad (1)$$

where  $P(Y_{ilfh} = 1)$  is the probability that the diagnosis is discordant with GT and  $Y_{ilfh}$  is the dichotomous outcome for case  $h$  ( $h = 1, 2, \dots, 250$ ), by reader  $f$  ( $f = 1, 2, 3, 4$ ), within site  $l$  ( $l = 1, 2, 3, 4$ ) using modality  $i$  ( $i = 1, 2$ ).

$\mu$  is the overall mean.

$\alpha_i$  is a fixed effect due to modality  $i$ ;  $\sum \alpha_i = 0$

$s_l$  is a random effect due to site  $l$ ;  $s_l \sim N(0, \sigma^2_s)$ , and the  $s_l$  are independent.

$r_{f(l)}$  is a random effect due to reader  $f$  nested within site  $l$ ;  $r_{f(l)} \sim N(0, \sigma^2_r)$ , and the  $r_{f(l)}$  are independent

$\beta_{h(l)}$  is a random effect due to case  $h$  nested within site  $l$ ;  $\beta_{h(l)} \sim N(0, \sigma^2_\beta)$ , and the  $\beta_{h(l)}$  are independent.

$\varepsilon_{ilfh}$  is the random error;  $\varepsilon_{ilfh} \sim N(0, \sigma^2_\varepsilon)$ .

The random components are independent from each other.

Using model (1), the difference in major discordance rate ( $\pi_{WSI} - \pi_{Glass}$ ) will be estimated and corresponding two-sided 95% confidence interval (CI) will be derived. If the upper bound of the 95% CI is less than the non-inferiority margin of 4%, then WSI will be considered non-inferior to Glass.

#### Supportive Analyses

The point estimates and the corresponding two-sided 95% CIs of the major discordance rates for both WSI and Glass will be estimated using model (1). To support the clinical performance of NanoZoomer, the modeled major discordance rate for WSI should not exceed 7%.

In addition, the observed, unmodeled major discordance rates for the two modalities, their difference and cross tabulation will also be presented.

For the observed data, details will be provided for cases for which the Glass diagnosis was concordant (including minor discordance) with the reference diagnosis and the WSI diagnosis was a major discordance for the same reader, or vice versa. The details will include case ID, reader ID, site, organ, case subtype/procedure, major discordance status for Glass, and major discordance status for WSI.

##### **11.1.2.1 Analysis of Non-inferiority Including Deferred Cases**

The primary endpoint analysis using the MMRM logistic regression model (1) will be repeated including deferred cases (excluding missing observations). In this analysis, deferred cases will be classified as having a minor discordance with GT.

##### **11.1.2.2 Sensitivity Analysis**

Sensitivity analyses will be performed to evaluate the robustness of the primary analysis results. To perform the sensitivity analyses, the primary analysis model (1) will be analyzed with the following assumptions for deferrals and missing data observations:

- a) All deferred plus missing data observations assumed as major discordance with GT.
- b) All deferred plus missing data observations for WSI assumed as major discordance with GT and All deferred plus missing data observations for Glass assumed as no major discordance with GT

#### **11.2 Secondary Objectives Analyses**

The AAP will be used for all secondary analyses. All secondary analyses will be descriptive in nature with no hypothesis testing. Missing reads and deferred reads will be excluded from these analyses.

##### **11.2.1 Accuracy by Site, Reader, Organ, and Case Subtype/Procedure**

###### **11.2.1.1 Accuracy by Site**

To describe the accuracy of WSI relative to Glass by site, the MMRM logistic model (1) with the omission of the site variable will be used. For each of the four sites, the estimated major discordance rates for the two modalities, their difference ( $\pi_{WSI} - \pi_{Glass}$ ), and their corresponding two-sided 95% CIs will be presented in

tabular format. In addition, cross tabulation of the observed, unmodeled major discordance rates for the two modalities will be presented as well.

#### 11.2.1.2 Accuracy by Reader

To describe the accuracy of WSI relative to Glass by reader, the MMRM logistic model (1) with the omission of reader and site variables will be used. The analyses will be the same as those for accuracy by site.

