**Table 2: FDA List of Cases to be tested for Primary Diagnosis Study**

(TOTAL 2000 CASES FOR THIS EXAMPLE)

CNB = Core Needle Biopsy; TUR = Transurethral Resection; LEEP = Loop Electrosurgical Excision Procedure; Dysp = Dysplasia; ECC = Endocervical Curettage; R/O = Rule Out;

ORGAN	# OF CASES	SUBTYPES (procedures)	
Gallbladder	10	10	
Appendix	10	10	
Soft Tissue Tumors	20	20	
Anus/Perianal	50	50	Bx
Miscellaneous to reach 2000	15	15	

Sponsor should include a sufficient number of difficult and challenging diagnoses in the larger (>100) groups

The total number of cases is to be 2000. The total cases are to be subdivided among the four (4) independent clinical sites (academic, community hospital, and private laboratories.) Each site will be assigned cases consistent with the types of cases read at that site and from the cases listed in [Table 2](#). The cases will be selected from actual cases diagnosed at that practice and taken from that site's own database.

However, it may be impractical for some sites to have sufficient cases of all types required under the protocol. In such eventuality, the PIs will review any gaps in cases enrolled across the study and propose adjustments of allotted cases at certain sites where some unbalance with respect to all numbers of cases for certain sites may occur. However, each site will enroll at least 400 cases and no more than 600 cases.

Ten extra cases at each site will be selected for self-familiarization testing after pathologist training. The selection of these ten cases will follow after the cases for the study have been collected.

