## 5. RANDOMIZATION AND BLINDING

### 5.1 Method of Assignment and Randomization

Randomization in this study refers to the order in which a given case will be read by a particular pathologist: Glass followed by WSI (GW) or WSI followed by Glass (WG) with at least 4 weeks between the two readings. In each site, half of the available cases will be randomly assigned to sequence GW and another half will be assigned to sequence WG. All 4 readers within each site will read both WSI and Glass for each case in that site. Randomization will occur in blocks such that there are an equal number of Glass cases and WSI cases read first within each block. The grouping of slides into containers at a site is a separate randomization to aid in operational management of the slides.

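### The by-reader analysis (SAP 11.2.1.2) does not say how its random-case model is fitted or turned into rates; with two reads per case that choice can decide the answer, and a paired-proportion interval avoids it.

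*SAP*

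**What the plan says.** In model (1) modality is a fixed effect, and "site, reader, and case will be included as random effects" (SAP 11.1.2, Primary Analysis Model). For accuracy by reader, SAP 11.2.1.2 states that "the MMRM logistic model (1) with the omission of reader and site variables will be used", with the same outputs as by site. The by-site section lists those outputs: "For each of the four sites, the estimated major discordance rates for the two modalities, their difference", with 95% intervals, plus a cross tabulation of observed rates. Once reader and site are removed, reader-specific results can only come from a separate fit for each reader.

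SAP 5.1 fixes the data available to each fit: "All 4 readers within each site will read both WSI and Glass for each case in that site". Each reader therefore contributes one Glass and one WSI read per case.

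SAP 11.3 names SAS 9.4 and nothing further. SAP 11.2.1.3 (organ) provides for non-convergence, and SAP 11.2.1.4 (subtype/procedure) drops the model because non-convergence is likely. SAP 11.2.1.2 does neither. SAP 11.2 makes all secondary analyses descriptive and excludes missing and deferred reads.

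Protocol 9.4.2.2 describes a different route. It takes the 16 by-reader differences and intervals from the primary model and reads their overlap in a forest plot as support for generalizability.

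**The concern.** A random case intercept estimated from pairs of rare binary outcomes is a hard case for the usual approximations to the likelihood. A second choice also matters: a rate can be read off at case effect zero (the typical case) or averaged over the case distribution. When cases differ widely, these are very different quantities. The SAP settles neither choice.

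Accuracy by reader is a declared secondary endpoint (SAP 3.2.2). The SAP promises a by-reader difference with an interval only through this model; the observed cross tabulation comes without one. If the chosen fit distorts the rates, the 16 modelled intervals will disagree with the counts printed beside them.

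**Working it through.** **Inputs from the documents.** Cases per reader: "each site will enroll at least 400 cases and no more than 600 cases" (Protocol 6.2); 500 is used as the centre. The correlation λ "is the correlation between the classifications for the two modalities by the same reader" (SAP 6) is 0.5 or 0.6 in SAP Table 2.

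**Assumed.** The documents give no expected major discordance rate. The only low figure is the supportive ceiling for WSI of 7% (SAP 11.1.2), so rates of 3-7% are assumed. λ = 0.3 was added as a milder case.

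**The plan's own figure.** There is none for the by-reader model. The limiting row of SAP Table 2 (agreement 0.6, λ 0.5, ξ−η 0.15, Δ −1.5%) confirms how λ enters:
- σ² = [0.6×0.4 + 0.615×0.385] × {1 − 0.5 + 3×0.15}/4 = 0.476775 × 0.95/4 = 0.11323
- n = (1.960 + 1.2816)² × 0.11323/0.025² = 1904, as printed.

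**One reader's table.** P(both discordant) = pW·pG + λ√[pW(1−pW)·pG(1−pG)]. At 5% in both modalities with λ = 0.5 this is 0.0025 + 0.5×0.0475 = 0.02625. Of 500 cases, about 13.1 are discordant on both reads, 11.9 on WSI only, 11.9 on Glass only and 463.1 on neither.

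**Fits of the modality plus random-case model** (WSI / Glass, %, 500 cases, λ = 0.5; expected tables unless marked):

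| True | Quadrature ML, averaged | Quadrature ML, effect 0 | Laplace, averaged | Laplace, effect 0 | Pseudo-likelihood, effect 0 |
|---|---|---|---|---|---|
| 5 / 5 | 5.00 / 5.00 | 0.083 / 0.083 | 20.5 / 20.5 | 0.005 / 0.005 | 4.13 / 4.13 |
| 6 / 4 | 6.0 / 4.0 | 0.10 / 0.04 | 23.4 / 18.3 | 0.007 / 0.001 | 5.1 / 3.1 * |
| 7 / 6 | 7.0 / 6.0 | 0.22 / 0.16 | 21.9 / 20.6 * | 0.008 / 0.004 * | 5.9 / 5.0 |

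\* Median of simulated readers. In the 6/4 simulations the observed medians were 6.0 / 3.8.

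- *Quadrature, averaged:* exact. Three parameters saturate a 2×2 table with three free cells.
- *Laplace, averaged:* 20.5/5 = 4.1-fold high. Over the table the range is 21.9/7 = 3.1 to 18.3/4 = 4.6. In the 6/4 row the estimated case SD is 13.1, and the difference is 23.4 − 18.3 = 5.1 points against a true 2.0.
- *Case effect zero, quadrature or Laplace:* near or below 0.1-0.2%. At true 5/4 the quadrature difference is 0.026 points against a true 1.0.
- *Pseudo-likelihood at the typical case:* 4.13/5 is 17% low. At true 5/4 the difference is 4.154 − 3.264 = 0.89 points against 1.0.
- *Convergence:* an undamped pseudo-likelihood routine failed in 89 of 120 simulated readers at 5/4 and in 32 of 120 at 7/6. A damped version converged on the expected tables on which it was run. These were hand-written routines, not SAS.

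**Sensitivity at true 5%.**
- λ 0.6: quadrature at zero 0.014%, Laplace averaged 22.9%, pseudo-likelihood 3.91% (22% low).
- λ 0.3: 0.70%, 16.8% and 4.54% (9% low).
- At a true rate of 40%, quadrature at zero gives 30.7% (λ 0.5), so the distortion is mainly a feature of rare discordance.

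**Paired interval.** At true 5/4, λ 0.5, the two one-sided cells are 0.02665 and 0.01665. SE = √[(0.0433 − 0.01²)/500] = 0.0093, a Wald half-width of 1.8 points; the mean Newcombe half-width is 1.97. Over 400-600 cases and the rates tried (20,000 simulations each), coverage was 94.2-95.7% for Wald and 95.5-96.6% for Newcombe. Newcombe half-widths at 500 cases were 1.7-2.3 points.

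**The case against.** The strongest reply is that the model, fitted well, gives the right answer. This stands. In 200 simulated readers at 6/4, quadrature averaged over cases matched the observed rates, its standard error for the difference matched the paired Wald value, and coverage was 95%. The SAP does not name Laplace or pseudo-likelihood, so it commits to no bad choice. It does not exclude one either.

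It also stands that little depends on the result. No test is attached. The observed cross tabulation carries over from the by-site section. SAP 11.1.2 (Supportive Analyses) also lists, with reader ID, every pair in which one modality is a major discordance and the other is not. A reader's WSI deficit would stay visible, and a case SD of 13 would expose a degenerate fit. Neither source promises an interval, however. Protocol 9.4.3 promises subgroup intervals, but names no method and does not list reader among its subgroups.

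Finally, SAP 11.2 excludes reads and not pairs, so a paired difference loses cases with one evaluable read, which the model would keep. That is a real but small cost.

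**Conclusion.** The concern holds as a specification gap with practical consequences. SAP 11.2.1.2 leaves open an estimation and back-transformation choice. At assumed discordance of 3-7% and λ = 0.5, permitted options range from exact, through roughly 10-25% low in relative terms (pseudo-likelihood at the typical case), to about 4-fold high at 5% (Laplace averaged) or near zero (case effect zero). The rates are assumptions; λ comes from the sample-size table.

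Three stronger readings are tempting and are not supported:
- A reader might infer that the model inherently gives rates several-fold wrong. It does not; the error depends on the fitting and averaging choice.
- A reader might infer that the plan cannot show whether someone does worse on WSI. The observed rates and the listing of discordant pairs show it, though without an interval.
- A reader might extend the point to the by-site analysis. There each case has up to 4 × 2 = 8 reads, and nothing calculated here applies to it.

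The primary analysis is not affected by this point.

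**What to change.** In SAP 11.2.1.2, for each reader:
- report observed Glass and WSI major discordance rates with Wilson 95% intervals over all evaluable reads;
- report the paired WSI−Glass difference with a Newcombe, Tango or Agresti-Min 95% interval (name one) over cases with both reads evaluable;
- state the number of incomplete pairs.

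If the model is kept, make it a supplement: quadrature, rates averaged over the case distribution, a named interval method, and the paired interval as the fallback for non-convergence.

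Reconcile the section with Protocol 9.4.2.2, so that the forest plot and the SAP table use one method.

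The cost is wording in the SAP, a matching change or cross-reference in the protocol, and simpler code. On complete pairs nothing is lost, because the best fit of the model gives the same estimate. The one downside is that single-read cases drop out of the difference.
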